6.4 BASELINE VISIT

Baseline screening of subjects can occur at the same visit of enrollment after the informed consent has been obtained. Subjects will be screened according to inclusion/exclusion criteria. Subjects will perform assessment of pain levels (VAS), quality of life (EQ-5D) and disability (ODI).

Subjects will be provided with a pain diary, instructed to fill it daily and return it at the SCS trial implant visit.

Clinical Investigational Plan

The following activities and assessments will be performed during baseline visit:

Timing of visit	Activities at visit	Case Report Form
Baseline	
Subject assessments of current pain levels, quality of life and disability	
• VAS Form• EQ-5D Form• ODI Form

6.5 SCS TRIAL IMPLANT

During the trial implant, two SCS leads will be implanted using standard surgical techniques. One lead will be implanted using paresthesia mapping to maximize the overlap between painful regions and evoked paresthesia according to standard clinical practice. A second lead will be implanted using a novel anatomical midline-based placement. Under fluoroscopic guidance the lead will be positioned above the anatomical midline such that it extends over the T9-T10 junction. No tonic stimulation based paresthesia mapping will be performed to implant this lead. Leads will be connected to the EPG such that channels 1-8 will provide stimulation through the paresthesia mapping-based lead and channels 9-16 to the anatomical midline-based lead.

Subjects will be randomized 1:1 to either lead sequence (paresthesia lead first followed by anatomical lead or vice versa). Only stimulation programs using the lead selected by the randomization will be programmed in the EPG. When programming stimulation delivered with the lead implanted using the paresthesia-based placement, paresthesia mapping will be used to define the optimal contacts to activate. When programming stimulation delivered with the lead implanted using the anatomical-midline placement, a generalized bipolar stimulation approach will be used.

During the programming sessions, burst stimulation amplitude will be slowly increased up to the point where the subject feels any stimulation induced sensation (paresthesia, warmth, heaviness, cramping); this intensity value will constitute the Threshold for Perception (TP). Intensity will be then set at 60% of TP and the subject will be asked to move around, walk and cough. If sensations are still experienced, amplitude will be reduced in 0.05 mA steps until no sensations are experienced during the aforementioned activities. This intensity level will be used to define the target intensity and the stimulator will be programmed to allow the subjects to increase stimulation intensity up to 80% of TP. Subjects will be instructed to increase stimulation intensity slowly (by one click every two hours) if they are not experiencing pain relief. Similarly, intensity should be reduced slowly if they are experiencing increased pain, uncomfortable stimulation, heaviness or any other side effects.

Subjects will be provided with a pain diary, instructed to fill it daily and return it at the trial assessment visit 1.

The following activities and assessments will be performed during SCS trial:

Timing of visit	Activities at visit	Case Report Form
SCS Trial	
SCS lead implantEPG programmingCollect stimulation parametersProvide pain diary	
• Surgery Form• Randomization Form• Programming Parameters Form• VAS Pain Diary Form

Clinical Investigational Plan

6.6 TRIAL ASSESSMENT 1

Two weeks after the start of the trial subject will assess therapeutic efficacy of the stimulation delivered using the lead assigned by randomization. Subjects will rate their level of pain using the VAS assessment, their quality of life using the EQ-5D questionnaire and their disability level using the ODI questionnaire.

Before any change is made, stimulation parameters used in the previous two weeks will be collected. Subsequently, subjects will cross over to stimulation delivered using the second lead. EPG stimulation programs used in the previous 2 weeks will be deleted and new stimulation programs will be programmed using the procedure detailed in the section 6.5.

Subjects will return the pain diary, be provided with a new one, instructed to fill it daily and return it at the trial assessment visit 2.

The following activities and assessments will be performed during end of anatomical lead trial visit:

Timing of visit	Activities at visit	Case Report Form
Trial Assessment 1	
Subject assessments of current pain levels, quality of life and disabilityCollect stimulation parametersEPG programmingCollect pain diaryProvide pain diary	
VAS FormEQ-5DODIProgramming Parameters FormVAS Pain Diary Form

6.7 TRIAL ASSESSMENT 2

At the end of the trial, subject will assess therapeutic efficiency of the stimulation delivered in the previous two weeks. Subjects will rate their level of pain using the VAS assessment, their quality of life using the EQ-5D questionnaire, their disability level using the ODI questionnaire and their preference. If the improvement in VAS obtained at either of the two trial assessment visits is $\geq 50\%$ of the baseline score, SCS trial will be considered successful and subjects will be considered for permanent IPG implant. Otherwise the subject will exit the study.

The following activities and assessments will be performed during end of anatomical lead trial visit:

Timing of visit	Activities at visit	Case Report Form
Trial Assessment 2	
Subject assessments of current pain level, quality of life and disabilityCollect stimulation parametersRecord subject preference between stimulation delivered using the 2 leadsCollect pain diary	
VAS FormEQ-5DODISubject Preference FormVAS Pain Diary Form

6.8 SCS IMPLANT PROCEDURE

IPG will be implanted using standard surgical techniques.

The following activities and assessments will be performed during SCS implant:

Clinical Investigational Plan

Timing of visit	Activities at visit	Case Report Form
SCS Implant	
IPG implant	
Surgery Form

6.9 ACTIVATION VISIT

The lead activated will depend on the subject's preference following the trial. If the subject has no preference, the lead placed using the anatomic midline-based technique will be activated. Stimulation intensity will be programmed with the same method used in the SCS trial implant visit.

Subjects will be provided a pain diary and instructed to complete it on the last week before the first follow up visit.

The following activities and assessments will be performed during activation visit.

Timing of visit	Activities at visit	Case Report Form
Activation	
IPG programmingProvide pain diary	
Programming Parameters form

6.10 SCHEDULED FOLLOW-UPS

Subjects will be followed up for 12 months. During each visit, the subjects will rate their level of pain using the VAS assessment, their quality of life using the EQ-5D questionnaire and their disability level using the ODI questionnaire. Stimulation parameters used will be collected before any change (if necessary) is made.

Subjects will return the pain diary, be provided a new one and instructed to complete it on the last week before the following follow up visit.

The following activities and assessments will be performed during follow up visits.

Timing of visit	Activities at visit	Case Report Form
Follow up	
Subject assess current pain levels, quality of life and disabilityCollect stimulation parametersCollect pain diaryProvide pain diary	
VAS FormEQ-5D FormODI FormProgramming Parameters FormVAS Pain Diary FormSubject Satisfaction Form

6.11 UNSCHEDULED VISITS

An Unscheduled Visit is defined as any visit where an active study subject returns to the participating study site for medical care outside of a specified study visit. Unscheduled visits may include subjects returning to the office for an adverse event.

The visit should be documented by completing the Unscheduled Visit Form and any other applicable forms (Adverse Event, Deviation, Death and/or Withdrawal Form).

Clinical Investigational Plan

6.12 DESCRIPTION OF ACTIVITIES PERFORMED BY SPONSOR REPRESENTATIVES

Trained sponsor personnel may perform certain activities to ensure compliance to the clinical investigational plan and may provide technical expertise.

Sponsor personnel may:

- Provide technical support to the Investigators during trial

Sponsor personnel will not:

- Perform the informed consent process
- Provide medical diagnosis or treatment to subjects
- Discuss a subject's condition or treatment with a subject without the approval and presence of a health care practitioner
- Independently collect clinical investigational data

6.13 SUBJECT STUDY COMPLETION

When the subject's participation in the clinical study has been completed the subject will return to the medical care as per physician's recommendation.

6.14 ANY KNOWN OR FORSEEABLE FACTORS THAT MAY COMPROMISE THE OUTCOME OF THE CLINICAL STUDY OR THE INTERPRETATION OF THE RESULTS

All foreseeable factors that may compromise the outcome have been taken into account by clinical study design and well-defined subject selection criteria.

Patient recruitment and retention will be monitored throughout the study and include (but are not limited to) the following activities: evaluation of the site and investigators, training of site personnel, developing site support materials, providing patient visit calendars.

6.15 CRITERIA AND PROCEDURES FOR SUBJECT WITHDRAWAL OR DISCONTINUATION

Subjects must be informed about their right to withdraw from the study at any time and for any reason without sanction, penalty or loss of benefits to which the subject is otherwise entitled and withdrawal from the study will not jeopardize their future medical care or relationship with the investigator. Subjects will be asked to specify the reason for the termination, but have the right not to answer.

The investigator may decide to withdraw a subject from the study at any time with reasonable rationale. The subject's future care will not be influenced by a decision, voluntary or otherwise, to withdraw from the study. All reasonable efforts should be made to retain the subject in the clinical study until completion of the study.

Reasons for subject's withdrawal include, but are not limited to:

- Subject refuses to continue participating in the study
- Subject does not meet the inclusion/exclusion criteria and does not require additional follow-up for safety reasons.
- Subject is deceased (cause must be documented)
- Subject's non-compliance
- Subject's participation is terminated by the PI or investigator, although the subject consented, since participation is no longer medically appropriate

Clinical Investigational Plan

- Subject is 'lost to follow up': Subject does not adhere to the scheduled follow up visits but has not explicitly requested to be withdrawn from the clinical study. (This does not apply to missed visits). Site personnel should at all times make all reasonable efforts to locate and communicate with the subject in order to achieve subject compliance to the scheduled follow up visits:
 1. A subject will be considered 'Lost to Follow Up' after a minimum of 2 phone calls of a physician or delegate at the investigational site to the subject or contact. These 2 phone calls need to be documented in the subject's hospital records.
 2. If these attempts are unsuccessful, a letter should be sent to the subject's last known address or general practitioner (GP) and a copy of this letter should be maintained in the subject's hospital records.

Note: If a subject misses one or more of the scheduled follow up visits (inclusive of the assigned visit windows), this will be considered as a missed visit. The subject may therefore still return for subsequent visits and will not be excluded from the study.

If a subject withdraws from the clinical study, the site will record the subject's reasons for withdrawal, on a Withdrawal CRF.

When subject withdrawal from the clinical study is due to an adverse event the subject will be followed until resolution of that adverse event or determination that the subject's condition is stable. The status of the subject's condition should be documented at the time of withdrawal.

The subject should be seen for a final study visit. At this final study visit, the subject will undergo the following evaluations:

- Identify and describe required evaluations or other procedures

7.0 COMPLIANCE TO CIP

7.1 STATEMENTS OF COMPLIANCE

The study will be performed in accordance with the most current versions of the World Medical Association (WMA) Declaration of Helsinki, ISO14155 and any regional and/or national regulations and will be compliant to this International Standard and any regional and national regulations, as appropriate.

The investigator will not start enrolling subjects or requesting informed consent from any subject prior to obtaining IRB/EC approval and Competent Authority approval, if applicable, and authorization from the sponsor in writing for the study.

In case additional requirements are imposed by the IRB/EC or Competent Authority, those requirements will be followed, if appropriate. If any action is taken by an IRB/EC, and regulatory requirements with respect to the study, that information will be forwarded to St. Jude Medical.

As sponsor, St. Jude Medical has taken up general liability insurance in accordance with the requirements of the applicable local laws. Appropriate country representative will be utilized to understand the requirements for the type of insurance that will be provided for subjects, such information will be incorporated into the informed consent, as applicable

Clinical Investigational Plan

If required, additional subject coverage or a study specific insurance will be provided by the Sponsor as well.

7.2 ADHERENCE TO THE CLINICAL INVESTIGATION PLAN

A deviation is defined as an event where the clinical investigator, site personnel, sponsor or sponsor representative did not conduct the clinical study according to the Clinical Investigational Plan, IRB/EC requirements or the Investigator Agreement. The investigator is not allowed to deviate from the CIP, except as specified under emergency circumstances.

In some cases, failure to comply with the CIP may be considered failure to protect the rights, safety and well-being of subjects, since the non-compliance exposes subjects to unreasonable risks. For example, failure to adhere to the inclusion/exclusion criteria: these criteria are specifically defined by the Sponsor to exclude subjects for whom the device is not beneficial and the use involves unreasonable risks. This may be considered failure to protect the rights, safety and well-being of the enrolled subject. Similarly, failure to perform safety assessments intended to detect adverse events may be considered failure to protect the rights, safety and well-being of the enrolled subject. Investigators should seek minimization of such risks by adhering to the CIP.

Simultaneously, in the event that adhering to the CIP might expose the subject to unreasonable risks, the investigator is also required to protect the rights, safety and well-being of the subject by intentionally deviating from the requirements of the CIP, so that subjects are not exposed to unreasonable risks.

It is the responsibility of the investigator to provide adequate medical care to a subject enrolled in a study.

Regulations require that the PI maintain accurate, complete, and current records, including documents showing the date of and reason for every deviation from the Clinical Investigational Plan. Relevant information for each deviation will be documented on a Deviation Case Report Form. The site will submit the CRF to St. Jude Medical.

Regulations require Investigators obtain approval from St. Jude Medical and the IRB/EC [as required] before initiating changes in or deviations from the protocol, except when necessary to protect the life or physical well-being of a subject in an emergency. Under emergency circumstances, deviations from the CIP to protect the rights, safety and well-being of human subjects may proceed without prior approval of the sponsor and the EC. Such deviations shall be documented and reported to the sponsor and the EC as soon as possible, but no later than 5 working days.

Prior approval must be requested when the PI anticipates, contemplates, or makes a conscious decision to depart from the CIP, except when unforeseen circumstances are beyond the investigator's control (e.g. a subject who fails to attend a scheduled follow-up visit, a subject is too ill to perform a CIP-required test, etc.). All deviations, including those beyond the investigator's control, must be reported on a CRF.

To obtain approval, the Principal Investigator may call or email and discuss the potential deviation with St. Jude Medical or designee prior to initiating any changes.

All deviations must be reported to appropriate regulatory authorities in specified timelines (if appropriate).

Clinical Investigational Plan

Investigators or the designee must notify St. Jude Medical, Inc. as soon as possible and complete the Deviation CRF.

The Investigator is required to adhere to local regulatory requirements for reporting deviations to IRB/EC.

7.3 REPEATED AND SERIOUS NON-COMPLIANCE

In the event of repeated non-compliance or a one-time serious non-compliance, as determined by the Sponsor, a Clinical Research Associate or clinical representative will attempt to secure compliance by one or more of the following actions:

- Visiting the investigator
- Contacting the investigator by telephone
- Contacting the investigator in writing
- Retraining of the investigator

If an investigator is found to be repeatedly non-compliant with the signed agreement, the CIP or any other conditions of the clinical study, the Sponsor will either secure compliance or, at its sole discretion, terminate the investigator's participation in the clinical study.

8.0 ADVERSE EVENT, ADVERSE DEVICE EFFECT, DEVICE DEFICIENCY

8.1 DEFINITIONS

8.1.1 Medical device

Any instrument, apparatus, implement, machine, appliance, implant, software, material or other similar or related article

- Intended by the manufacturer to be used, alone or in combination, for human beings for one or more of the specific purpose(s) of
 - Diagnosis, prevention, monitoring, treatments or alleviation of disease,
 - Diagnosis, monitoring, treatment, alleviation of, or compensation for, an injury,
 - Investigation, replacement, modification, or support of the anatomy or of a physiological process,
 - Supporting or sustaining life,
 - Control of conception,
 - Disinfection of medical devices and
- Which does not achieve its primary intended action in or on the human body by pharmacological, immunological or metabolic means, but which may be assisted in its intended function by such means

8.1.2 Adverse Event (AE)

Any untoward medical occurrence, unintended disease or injury, or untoward clinical signs (including abnormal laboratory findings) in subjects, users or other persons, whether or not related to the investigational medical device under study.

This definition includes events related to the investigational medical device or the comparator. This definition includes events related to the procedures involved.

Clinical Investigational Plan

8.1.3 Serious Adverse Event (SAE)

An adverse event that led to:

- Death
- A serious deterioration in the health of the subject, that either resulted in:
 - A life-threatening illness or injury OR
 - A permanent impairment to a body structure or a body function OR
 - An in-patient or prolonged hospitalization OR
 - A medical or surgical intervention to prevent life-threatening illness or injury or permanent impairment to a body structure or a body OR
 - A malignant tumor
- Fetal distress, fetal death or a congenital abnormality or birth defect

A planned hospitalization for a pre-existing condition, or a procedure required by the CIP is not considered a serious adverse event.

8.1.4 Adverse Device Effect (ADE)

An adverse event related to the use of an investigational medical device.

This definition includes adverse events resulting from insufficient or inadequate instructions for use, deployment, implantation, installation, or operation, or any malfunction of the investigational medical device.

This definition includes any event resulting from the use error or from intentional misuse of the investigational medical device.

8.1.5 Serious Adverse Device Effect (SADE)

Adverse device effect that has resulted in any of the consequences characteristic of a serious adverse event.

1. Unanticipated Serious Adverse Device Effect (USADE) [applicable to studies following ISO 14155]

A serious adverse device effect which by its nature, incidence, severity or outcome has not been identified in the current version of the risk analysis report.

2. UADE [applicable to investigational studies following FDA regulations]

As defined in 21 CFR §812.3, unanticipated adverse device effects (UADE) are defined as any serious adverse effect on health or safety or any life-threatening problem or death caused by, or associated with, a device, if that effect, problem, or death was not previously identified in nature, severity, or degree of incidence in the clinical investigational plan or application (including a supplementary plan or application), or any other unanticipated serious problem associated with a device that relates to the rights, safety, or welfare of subjects.

If an unanticipated adverse device effect occurs, the investigator must notify St. Jude Medical and the IRB/MEC immediately, but no later than 10 working days of the investigator's knowledge of the event, as required by 21 CFR §812.150. St. Jude Medical will take any steps necessary to investigate the event, and will be responsible for notifying FDA and all other participating IRBs/MECs and investigators.

Clinical Investigational Plan

3. Anticipated Serious Adverse Device Effect (ASADE)

A serious adverse device effect which by its nature, incidence, severity or outcome has been previously identified in the risk analysis report.

8.2 PROCEDURE FOR ASSESSING, RECORDING, AND REPORTING ADVERSE EVENTS, DEVICE DEFICIENCIES/COMPLAINTS, ADVERSE DEVICE EFFECTS, SERIOUS ADVERSE EVENTS, AND SERIOUS ADVERSE DEVICE EFFECTS:

Safety surveillance within this study and the safety reporting both performed by the investigator, starts as soon as the subject is enrolled in this study (date of signature of the informed consent). The safety surveillance and the safety reporting will continue until the last investigational visit has been performed, the subject is deceased, the subject/investigator concludes his participation into the study or the subject/investigator withdraws the subject from the study, except as otherwise specified in the CIP.

All adverse event data including deaths and device deficiency data (if applicable) will be collected throughout the clinical study and will be reported to the Sponsor on a dedicated case report form. The Investigator will record all adverse events and device deficiencies on the appropriate case report forms.

Records relating to the subject's subsequent medical course must be maintained and submitted (as applicable) to the Sponsor until the event has subsided or, in case of permanent impairment, until the event stabilizes and the overall clinical outcome has been ascertained. Adverse events will be monitored until they are adequately resolved. The status of the subject's condition should be documented at each visit.

The investigator will report the event to the IRB/EC per their reporting requirements.

Reportable events to sponsor are considered:

- All Adverse Device Effects
- All Serious Adverse Events (whether or not the event is considered device or procedure related and regardless the randomization group)

All above events will be reported to the Sponsor, as soon as possible, but no later than 72 hours of first learning of the event.

The Sponsor will ensure that all events and device deficiencies are reported to the relevant authorities as per regulations.

Adverse events needs to be reported using the adverse events CRF specifying date of the adverse event, treatment, resolution, assessment of both the seriousness and the relationship to the investigational device, type of treatment and status of the adverse event.

Additional information may be requested, when required, by the Sponsor in order to support the reporting of AEs to regulatory authorities.

The investigator must notify the IRB/EC, if appropriate, in accordance with national and local laws and regulations, of the AEs reported to the Sponsor.

Clinical Investigational Plan

All adverse events will be reported as per applicable regulatory requirements.

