3.3 ANTICIPATED ADVERSE EVENTS AND ADVERSE DEVICE EFFECTS

In addition to those risks commonly associated with surgery, the following risks are associated with implanting or using this neurostimulation system for SCS:

Anticipated adverse events
Undesirable changes in stimulation, which may be related to cellular changes in tissue around the electrodes, changes in electrode position, loose electrical connections, or lead failure
Lead migration, causing changes in stimulation and/or reduced pain relief
Epidural hemorrhage, hematoma, infection, spinal cord compression, or paralysis from placement of a lead in the epidural space
Cerebrospinal fluid (CSF) leakage
Paralysis, weakness, clumsiness, numbness, or pain below the level of the implant
Persistent pain at the electrode or IPG site
Seroma (mass or swelling) at the IPG site
Infection of the lead extension at the exit zone during trial or infection of the IPG site
Allergic or rejection response to implant materials
Implant migration or skin erosion around the implant
Anticipated adverse device effects
Battery failure
Battery leakage

These adverse events and adverse device effects are not specific to the study, but related to the approved SCS implant procedure.

Clinical Investigational Plan

3.4 RESIDUAL RISKS ASSOCIATED WITH THE DEVICE UNDER INVESTIGATION, AS IDENTIFIED IN THE RISK ANALYSIS REPORT

There are no residual risks associated with the stimulation protocol under investigation.

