If the VAS score during either of the two trial assessments is reduced by at least 50% compared to the baseline score, the subject will be considered for permanent SCS implant. Subjects who do not experience a $\geq 50\%$ overall pain relief on either of the 2 leads will exit the study.

Subjects who underwent a successful trial ($\geq 50\%$ overall pain relief) will then be implanted with a SJM Proclaim™, Prodigy™ or Prodigy MRI™ system. The lead activated will depend on the subject's preference following the trial. If the subject has no preference; the lead placed using the anatomic midline-based technique will be activated. The subject will then be followed for 12 months to assess the long term treatment outcome. Follow up visits will occur at 3, 6 and 12 months after permanent implant. During each of these visits, subjects will rate their pain using the VAS, their quality of life using the EQ-5D, their disability using the ODI.

The total duration of the study is expected to be approximately 2 years.

The clinical study will be conducted in up to 3 centers in the E.U.

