12.2 SAMPLE SIZE

Approximately 50 patients will be enrolled in this study. Based on clinical experience atleast 80% of the subjects are expected to have a successful trial and be implanted with permanent IPGs. Enrollment will be discontinued after 40 subjects have received a permanent implant. This study is a feasibility trial; the sample power cannot be calculated because the effect size is not known. The sample size was selected to obtain early evidence and estimates of the effect size.

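### New adverse events at or after lead removal need not be captured in subjects who exit without a permanent implant

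*Combined protocol and SAP*

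**What the plan says.** Section 8.2 starts safety surveillance at consent and then sets its end: "The safety surveillance and the safety reporting will continue until the last investigational visit has been performed". The alternative end points are death, withdrawal, or the moment when "the subject/investigator concludes his participation into the study". The rule carries one reservation, "except as otherwise specified in the CIP".

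Section 6.5 describes the start of the trial phase: "During the trial implant, two SCS leads will be implanted using standard surgical techniques". Section 6.7 applies the 50% relief test at Trial Assessment 2 and disposes of failures in one line: "Otherwise the subject will exit the study". Section 4.2 agrees: subjects without at least 50% "overall pain relief on either of the 2 leads will exit the study".

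Among the anticipated events, section 3.3 lists "Infection of the lead extension at the exit zone during trial or infection of the IPG site", and also epidural haemorrhage, haematoma and CSF leakage.

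On numbers, section 12.2 plans about 50 enrolled, stops enrolment at 40 permanent implants, and says that "atleast 80% of the subjects are expected to have a successful trial and be implanted with permanent IPGs".

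**The concern.** A subject who fails the trial has had two epidural leads, and on the plan's schedule about four weeks of stimulation. Such a subject reaches the last scheduled visit, and the end of participation, at Trial Assessment 2. Taking the leads out is a further procedure, and some of its complications would show only days later. If the plan's own stopping rule is followed to the letter, nobody is required to ask about them or report them.

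The gap is uneven. Subjects who go on to a permanent implant are observed for 12 months after activation, while those who exit have no defined follow-up. Section 3.8 says that participation carries no more risk than standard treatment, and incomplete ascertainment in exiting subjects weakens any check of that statement. Section 7.2 itself treats omission of safety assessments meant to detect adverse events as a possible failure to protect subjects.

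**Working it through.** **Step 1: is there a capture route for a new event after exit?** The provisions that might supply one are:

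- *Visit schedule (6.2 to 6.10).* No activity table or form list mentions lead removal or a contact after it.
- *Reservation in 8.2.* No other section uses it for trial failures or for lead removal.
- *Monitoring of events to resolution (8.2), and follow-up when an adverse event causes withdrawal (6.15).* Both apply to events that have already begun.
- *Unscheduled visits (6.11).* These are limited to active subjects, so not to those who have exited.
- *Final study visit (6.15).* It is written for withdrawals. Trial failure is not among the listed reasons, although the list is not exhaustive. No timing is given, and the evaluations are an unfilled template instruction.

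None of these requires capture of an event that first appears after a trial failure has exited.

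**Step 2: are the leads in place up to Trial Assessment 2?** This is inferred. Stimulation through the second lead runs for the two weeks before that visit, and the parameters are collected there (6.7). The permanent procedure lists only the pulse generator (6.8), and activation then selects one of the leads (6.9). The leads therefore appear to be kept until the success decision. The removal date is not stated.

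**Step 3: does the timing of removal matter?** There are two cases:

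- Removal after the visit: both the procedure and its aftermath fall outside the window.
- Removal at the visit: events on the day are covered, because surveillance runs until the visit has been performed. A complication that appears later is still outside.

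The gap for later events is present in both cases.

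**Step 4: how many subjects?** First the plan's own figure: 40 / 0.80 = 50 enrolled, which reproduces section 12.2 and implies 50 − 40 = 10 without a permanent implant. With N = 40 / s rounded up, where s is the success rate:

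| Success rate s | Enrolled N | Without implant, N − 40 | Share |
|---|---|---|---|
| 70% (below the plan's floor) | 58 | 18 | 31% |
| 80% (the plan's floor) | 50 | 10 | 20% |
| 85% | 48 | 8 | 17% |
| 90% | 45 | 5 | 11% |
| 95% | 43 | 3 | 7% |

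**Step 5: how likely is at least one uncaptured event?** The documents give no removal-event rate, so the per-subject risk r is an assumption. The formula is 1 − (1 − r)^m for m exiting subjects.

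| Assumed r | m = 10 | m = 5 |
|---|---|---|
| 2% | 1 − 0.98^10 = 18% | 10% |
| 5% | 1 − 0.95^10 = 40% | 23% |
| 10% | 1 − 0.90^10 = 65% | 41% |

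For a given r and m these are upper bounds. They assume that every exiting subject has leads to remove and that nothing is picked up by a same-day observation or a final visit.

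**The case against.** The strongest answer is section 6.15. Its final study visit is stated generally, and the list of withdrawal reasons is open-ended, so an exiting trial failure could be read into it. Surveillance would then stay open until that visit. This stands as a possible reading, and it is why the sections need reconciling. It does not close the gap: the visit has no content and no timing relative to removal, and 8.2 also allows surveillance to end when participation concludes.

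A reader might infer three stronger things that the documents do not support.

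- *That reporting demonstrably closes before the leads come out.* No removal date is given, and removal at Trial Assessment 2 is not ruled out. The flow charts in 1.1 and 6.1 were not legible in the text available, and the case report forms are held separately (Appendix F).
- *That these events are never captured, in about 1 in 5 subjects.* Events open at exit are followed to resolution, and a site may report more than it must. The 80% is a floor, so 10 of 50 is the most that the plan expects. The remainder can also include withdrawals and subjects not implanted for other reasons.
- *That a planned safety rate will be biased downwards, through trial failures alone.* No objective or endpoint in 4.3 and 4.4 is a safety rate, and section 12 plans no safety analysis. A subject who withdraws with leads in place is in the same position as a trial failure.

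It is also fair to say that the devices are market-released and that 3.3 describes the listed events as not specific to this study. That lowers the stakes, but the plan still undertakes to collect all adverse events throughout the study.

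**Conclusion.** The point holds as an omission in the reporting rule. For subjects who exit without a permanent implant, a new event at or after lead removal has no required route into the data. The affected group is up to about 10 of 50 at the plan's floor of 80% success and about 5 of 45 at 90%. It would be larger only if success fell short of the plan's own expectation.

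The conclusion rests on one inference, that the trial leads stay in until the success decision. It does not depend on the day of removal, because later-onset events are missed either way. The 18%, 40% and 65% figures rest on assumed risks and serve only to show that at least one uncaptured event is plausible. They do not estimate how many will occur. The primary comparison of pain relief is not affected. The change is worth making because it is specific and cheap.

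**What to change.** Reconcile sections 6.7, 6.15 and 8.2:

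- In 8.2, state that for subjects who exit or withdraw without a permanent implant, adverse event reporting continues through lead removal and for a fixed period afterwards, set by the sponsor. Close it with one documented contact.
- In 6.7, refer to that rule where the exit of trial failures is stated.
- In 6.15, say whether the final study visit applies to trial failures, and complete the blank list of evaluations.
- Record the removal date on a case report form, for example the existing Surgery Form.

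This changes reporting only and sets no rule on when or how leads are removed. On the plan's own assumption it costs at most about 10 extra contacts and as many form entries.
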